7.4.2.3. Time to First Negative Blood Culture

Time to first negative blood culture is defined as the number of days from first dose date of study drug to the date of first negative blood culture plus 1.

Time to first negative blood culture will be summarized in total using descriptive statistics for the MITT and PP Population.

In addition, the Kaplan-Meier estimate of the median time to first negative blood culture and the associated 95% confidence interval will be presented. Patients without a negative blood culture at post-baseline visits will be censored at the last assessment date.

7.4.2.4. Overall Survival at Study Day 30

Overall survival at Study Day 30 is defined as patient alive by study day 30.

The number of percentage of patients alive or dead by Study Day 30 will be summarized for the MITT and PP Population.

Time to death is defined as the number of days from first dose date of study drug to the date of death from any cause plus 1. Patients without death or lost to follow-up will be censored on the last date the patient is known to be alive. The Kaplan-Meier estimate of the median time to death and the associated 95% confidence interval will be presented.

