4.3 Dosing Criteria

Patients must meet the following criteria to begin dosing:

1. Confirmed diagnosis of candidemia
2. Received ≤ 2 days (≤ 48 hours) equivalent of prior systemic antifungal treatment at approved doses to treat the current episode of candidemia

OR

≤ 5 days (≤ 120 hours) equivalent of prior treatment for candidemia caused by *Candida* spp. with documented resistance to the specific prior antifungal administered

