6.4 Treatment Period

6.4.1 Baseline (Day 1 Pre-Dose)

Baseline procedures are to be completed pre-dose on the same day as the first dose of study drug (Day 1). The following procedures will be performed at Baseline (Day 1 Pre-dose):

- Confirm inclusion/exclusion criteria
- Perform APACHE II score calculation (Appendix C)
- Record vital signs, including temperature, blood pressure, heart rate, respiratory rate, oxygen saturation, and weight; height will be collected (from the patient's medical record) at Baseline
- Intravascular catheter management and log of the line changes; any indwelling intravascular catheters should be removed and catheter tips cultured prior to starting APX001 dosing; entrance site tissue should also be cultured if it appears infected
- Perform clinical laboratory assessments (serum chemistry, hematology, coagulation, and urinalysis)
- Perform 12-lead ECG
- Perform urine pregnancy test (for females of childbearing potential only)
- Perform complete physical examination including an assessment of general appearance, skin, eyes, heart, chest, abdomen, the body site that corresponds to the entry site of candidemia (e.g., central venous catheter entry site), and a neurological examination.
- Collect blood culture for *Candida* spp. and blood for *Candida* spp. testing by T2MR assay
- Collect plasma sample for PK (APX001 [prodrug] and APX001A [active moiety])
- Collect other cultures and histopathology from other sites, as clinically indicated to monitor the site(s) and extent of candidemia infection
- Perform imaging tests, as clinically indicated to monitor the site(s) and extent of candidemia infection

- Collect serum samples for analysis of (1,3)- β -D-glucan
- Record concomitant medications
- Record adverse events

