7.1.3. Baseline Definition

For microbiological data, baseline pathogen(s) are *Candida spp*. isolated from the last positive blood sample collected within 96 hours prior to the first dose of study drug.

For all efficacy and safety endpoints, baseline is defined as the last measurement or assessment prior to the first dose of study drug.

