7.2.3. Modified Intent-to-Treat (MITT) Population

The MITT Population will include all patients who satisfy the following criteria:

- Receive at least 1 dose of study drug; and
- Have a confirmed diagnosis of candidemia (blood culture positive for *Candida* spp.) within 96 hours of the start of treatment with APX001

The MITT Population will be the primary population used for the efficacy analysis.

7.2.4. **Per-Protocol (PP) Population**

The Per-Protocol Population will include all patients who satisfy the following criteria:

- Received at least 1 dose of study drug;
- Have a confirmed diagnosis of candidemia within 96 hours of the start of treatment with APX001;
- Did not exceed prior antifungal treatment (per eligibility assessed by the DRC);
- Meet the protocol's key inclusion and exclusion criteria; and
- Have no major protocol violations.

Based on the above criteria, the validity listings will be provided to identify which patients to be excluded from the PP Population. After the study team's review, the decision to exclude a patient from the PP Population will be finalized and a list of patients with major protocol deviations leading to exclusion from the PP Population will be finalized and documented.

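### Time to first negative blood culture includes patients already culture-negative before the first dose; a supportive estimate in still-positive patients and a count of the others should be added (minor)

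*SAP*

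**What the plan says.** SAP 7.4.2.3 defines the endpoint as "the number of days from first dose date of study drug to the date of first negative blood culture plus 1". On the analysis set it says: "Time to first negative blood culture will be summarized in total using descriptive statistics for the MITT and PP Population". A Kaplan-Meier median with a 95% confidence interval is added, and the censoring rule reads: "Patients without a negative blood culture at post-baseline visits will be censored at the last assessment date".

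Four other provisions decide who enters this analysis:

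- SAP 7.2.3 admits to MITT a dosed patient with a positive blood culture "within 96 hours of the start of treatment with APX001". Neither it nor the PP definition in SAP 7.2.4 asks that the last culture before dosing be positive.
- SAP 7.1.3 takes the baseline pathogen as the Candida "isolated from the last positive blood sample collected within 96 hours prior to the first dose of study drug". That is the last positive sample, not the last sample. For efficacy and safety endpoints in general, "baseline is defined as the last measurement or assessment prior to the first dose of study drug".
- Protocol 4.3 allows dosing after up to 48 hours "equivalent of prior systemic antifungal treatment at approved doses to treat the current episode of candidemia", and Protocol 5.6.2 repeats the limit. Up to 120 hours is allowed where resistance to the drug given is documented.
- SAP 6.5.1 requires cultures at screening and again at Baseline before dosing, then daily through Study Day 4.

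Two planned outputs touch on the matter. SAP 7.4.3 tabulates Candida species from blood culture by visit from Baseline, and SAP 7.3.6 tabulates prior antifungals. Neither feeds an estimate of clearance time.

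**The concern.** The clock starts at the first APX001 dose, but a patient's bloodstream may already have cleared by then. Species identification takes time, other antifungals may be given meanwhile, and Protocol 6.4.1 asks for catheters to be removed before dosing. Such a patient still qualifies through the earlier positive culture. Because a Day 2 culture is required, the patient normally enters as an event on Day 2, the earliest value a post-dose negative can usually take.

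The result is a median that mixes clearance on APX001 with clearance that came before it. Apart from patients who regrow, the mixing pulls the median downwards. With one arm, no comparator group carries the same distortion, and a larger sample would not remove it. What is at stake is how the reported clearance time is read; no test or decision rule depends on it.

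**Working it through.** The plan states no expected clearance time for this trial and no sample-size calculation, so there is no figure of its own to reproduce. The check asks how many patients could be affected and how far the median would move.

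**Inputs from the documents.** About 20 patients (SAP 3). Median clearance of 2 to 3 days after appropriate therapy, from earlier trials (Protocol 5.2.3). Up to 48 hours of prior therapy (Protocol 4.3). Daily cultures from Day 2 (Protocol 6.4.2).

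**Assumptions.** Clearance time is exponential with median m. Effective prior therapy lasts a time t uniform over 0 to 2 days. Catheter removal and the 120-hour allowance are not counted; the latter needs documented resistance to the drug given.

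**Step 1: share already negative at dosing.** The mean of 1 − 2^(−t/m) over t from 0 to 2 is 1 − [m/(2 ln 2)] × [1 − 2^(−2/m)].

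- m = 2: 1 − 1.443 × 0.500 = 0.279
- m = 2.5: 1 − 1.803 × 0.426 = 0.232
- m = 3: 1 − 2.164 × 0.370 = 0.199

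If every patient had effective prior therapy, 20 to 28% would be already negative, or 4.0 to 5.6 of 20. If half did, the share is 10 to 14%, or 2.0 to 2.8 of 20.

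**Step 2: effect on the median.** In 100,000 simulated trials of 20 patients without censoring, k patients were negative before dosing and scored Day 2. The other patients were first negative on Day 1 + ceil(T), with T exponential with median m. The Kaplan-Meier median is the 10th ordered value. Average medians, in days on the SAP scale:

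| Clearance median m | k = 0 | k = 2 | k = 3 | k = 4 |
|---|---|---|---|---|
| 2 days | 3.4 | 3.1 | – | 2.8 |
| 2.5 days | 3.9 | 3.5 | 3.3 | 3.1 |
| 3 days | 4.4 | 4.0 | – | 3.5 |

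For m = 2.5 the means are 5.1, 4.8, 4.7 and 4.5. Averaging the 10th and 11th values instead gives medians of 4.09, 3.72, 3.52 and 3.31, so the shift is unchanged.

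**Step 3: regrowth.** If each pre-dose negative has a 25% chance of a positive Day 2 culture and is then scored at Day 2 + ceil(T), the medians for m = 2.5 are 3.7 (k = 2) and 3.4 (k = 4).

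**Step 4: visibility in one trial.** For m = 2.5, 95% of single-trial medians lie in 3 to 6 days with k = 0, and in 2 to 5 with k = 2 or 4. Within the same trial and without regrowth, the all-MITT median is below the still-positive median in 34% of trials (k = 2) and 63% (k = 4), and above it in none. With k = 2 the two differ by 2 days or more in about 2% of trials.

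**Step 5: what the still-positive subset measures.** The exponential model has no memory, so it gives still-positive patients neither a head start nor a handicap. If clearance rates differ between patients, those still positive after prior therapy are on average slower. With everyone pre-treated and gamma-distributed rates (shape 2 or 1, overall median held at 2.5 days), the median time from dosing in the subset rises to about 2.9 and 3.3 days respectively.

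**The case against.** The strongest reply is that nothing in the documents shows that any patient is affected, and that little would follow if some were. The share rests on assumed prior therapy and an assumed clearance curve. With 2 patients affected the two medians coincide in about two trials out of three. The endpoint is one of several secondary parameters, summarised descriptively, with no test, threshold or planned comparison. The species-by-visit table should give the number with no growth at Baseline, apart from missing cultures, and patient listings are planned. Counting from first dose in the primary efficacy population is a defensible choice. All of this stands, and it is why the point is minor.

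It is also fair that restricting to still-positive patients does not isolate the effect of APX001. Those patients may carry over benefit from up to 48 hours of other drugs, and they are selected on response to that therapy.

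What the reply does not answer is that no planned clearance estimate separates these patients. A reader of the reported median alone could not tell how much of it reflects clearance before the first dose.

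Three stronger readings are tempting and not supported:

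- A reader might infer that a pre-dose negative is itself the event, giving values of 1, 0 or below. The event sentence does not say post-dose, but the baseline definition and the censoring sentence imply it. Scoring these patients as Day 1 or Day 2 gives the same medians in the cases above.
- A reader might infer that the primary result is compromised. Treatment Success at EOST does not use this estimate.
- A reader might infer that the still-positive estimate should replace the all-MITT one. Step 5 shows why it should not.

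**Conclusion.** The point holds as a minor one. As written, SAP 7.4.2.3 includes any MITT or PP patient whose last pre-dose culture was negative, and such patients tend to shorten the reported clearance time without showing clearance on APX001. For 2 to 4 such patients among 20 and a 2.5-day clearance median, the average Kaplan-Meier median falls by about 0.4 to 0.8 day (3.9 to 3.5 and 3.1), or by about 0.2 to 0.5 day if a quarter regrow on Day 2. These sizes rest on exponential clearance, no censoring and an assumed number of patients. The direction follows from the definitions, with an occasional exception when a patient regrows. The documents do not support calling this a material bias: the shift lies within single-trial variation, and the endpoint is descriptive and secondary.

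**What to change.** In SAP 7.4.2.3:

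1. Keep the all-MITT estimate as planned.
2. Add a supportive Kaplan-Meier estimate, with its 95% confidence interval, in MITT patients whose last pre-dose culture was positive.
3. Report beside it the number whose last pre-dose culture was already negative.

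Define the last pre-dose culture by date and time, since screening cultures may be drawn on the dosing day. It is the Baseline culture or, if that is missing, the latest screening draw, and it is positive if any set from that draw grew Candida.

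The cost is a few lines of SAP text, one estimate and one count, all from data already collected. The subset is fixed before dosing, so it adds no selection on events after APX001 starts.

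The SAP should state the downsides. About 16 to 18 patients would remain if 2 to 4 are negative. One negative culture is not proof of clearance, so the groups should be labelled by culture status. Still-positive patients may carry over prior therapy. The subset is selected on response to that therapy and may over-represent slow clearers, so neither estimate should be quoted without the other.

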6.4. Definitions for Efficacy Assessments

6.4.1. At End of Study Drug Treatment (EOST)

Treatment Success is defined as meeting all of the following criteria:

- Two consecutive blood cultures negative for *Candida* spp.;
- Alive at EOST; and
- No concomitant use of any other systemic antifungal therapies through EOST.

Treatment Failure is defined as any case that does not meet the criteria for Treatment Success.

Mycological Outcome:

• Eradication is defined as a negative blood culture(s) for *Candida* spp. in the absence of concomitant antifungal therapy through EOST.

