7. STATISTICAL METHODOLOGY

7.1. General Considerations

7.1.1. Summary Statistics

Summary statistics will be presented in total. For continuous variables, the number of observations (n), mean, standard deviation, median, minimum, and maximum will be provided. For categorical variables, the frequency and percentage in each category will be displayed.

For summary statistics, the mean and median will be displayed to one decimal place greater than the original value and the measure of variability (e.g. standard deviation) will be displayed to two decimal places greater than the original value.

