7.1.2. Handling of Dropouts and Missing Data

Subjects who dropped out or had missing outcome data will be included in the denominator for efficacy analyses. A clinical failure occurring at an earlier time point will be carried forward to the subsequent visits.

In cases of missing or incomplete dates (e.g. Adverse event [AE] and concomitant medications), the missing component(s) will be assumed as the most conservative value possible. For example, AEs with missing start dates, but with stop dates either overlapping into the treatment period or missing, will be counted as treatment-emergent, taking the worst-case approach. When partial dates are present in the data, both a partial start date and/or a partial stop date will be evaluated to determine whether it can be conclusively established that the AE started prior to the start of study drug or ended prior to the start of study drug. If the above cannot be conclusively established based on the partial and/or present dates, then the AE will be considered as treatment-emergent. Actual data values as they appear in the original eCRF will be presented in the data listings.

Missing values for other variables will not be imputed and only observed values will be used in data analyses and summaries.

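### Time to first negative culture: the descriptive summary covers only patients who had a negative, and one unconfirmed negative counts as the event; the time-to-event estimate should lead

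*SAP*

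**What the plan says.** SAP 7.4.2.3 defines the endpoint as "the number of days from first dose date of study drug to the date of first negative blood culture plus 1". It then plans two summaries.

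- **Descriptive.** "Time to first negative blood culture will be summarized in total using descriptive statistics for the MITT and PP Population". SAP 7.1.1 says what this means for a continuous variable: "the number of observations (n), mean, standard deviation, median, minimum, and maximum will be provided".
- **Kaplan-Meier.** "In addition, the Kaplan-Meier estimate of the median time to first negative blood culture and the associated 95% confidence interval will be presented". The censoring rule comes next: "Patients without a negative blood culture at post-baseline visits will be censored at the last assessment date".

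Two rules in SAP 7.1.2 bear on the descriptive summary. One is a denominator rule: "Subjects who dropped out or had missing outcome data will be included in the denominator for efficacy analyses". The other closes that section: "Missing values for other variables will not be imputed and only observed values will be used in data analyses and summaries".

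Elsewhere the plan asks for more than one negative. Treatment Success in SAP 6.4.1 requires "Two consecutive blood cultures negative for" *Candida* species. SAP 6.5.1 requires daily cultures on Study Days 1 to 4 and lets them stop only after negatives on two consecutive days. Protocol 5.2.3, citing treatment guidelines, also describes documented clearance in terms of consecutive negatives.

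**The concern.** Two features push the reported time in the same direction.

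First, a mean or median of observed times can use only patients who have a time. A patient whose cultures stay positive has none. The denominator rule does not help, because it assigns no time to that patient. The descriptive table is therefore conditional on having had a negative, and the SAP plans no label that says so. The report will carry two medians for one endpoint, with no statement of which is the main one.

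Second, one negative ends the clock. If that negative is false and the next culture is positive, the patient still counts as cleared on the earlier day. Kaplan-Meier does not repair this, because the patient enters it as an event.

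The study has no comparator, so a reader has only the absolute time and will tend to set it against the median of 2 to 3 days that Protocol 5.2.3 cites from earlier trials. A shift of a day or more would change that comparison.

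**Working it through.** The documents give no figure for this endpoint, so there is nothing to reproduce. What follows is illustration. From the documents come the 2 to 3 day median (Protocol 5.2.3), the 14-day treatment period, the daily cultures and the sample of about 20. Everything else is assumed.

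**1. A 20-patient example.** Suppose clearance days are 1, 1, 2 (five patients), 3 (five), 4 (three), 5, 5, 6, 7, 8.

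- All clear: mean = 70/20 = 3.50 days, median 3.
- The four slowest (5, 6, 7, 8) never clear: descriptive mean = (70 − 26)/16 = 2.75; descriptive median still 3.
- The six slowest (4, 5, 5, 6, 7, 8) never clear: mean = (70 − 35)/14 = 2.50; median 2.5.
- Kaplan-Meier, with never-clearers censored at Day 14: the proportion not yet cleared is 13/20 = 0.65 after Day 2 and 8/20 = 0.40 after Day 3. The median is 3 in every case.

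The descriptive mean moves readily; the descriptive median may or may not.

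**2. Perfect cultures, a fraction q never clearing.** Let clearance among the rest be exponential with median m. The descriptive median is about m. The Kaplan-Meier median t solves (1 − q)(1 − 2^(−t/m)) = 0.5, so t = −m × log2(1 − 0.5/(1 − q)).

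| q | m = 2 days | m = 3 days |
|---|---|---|
| 10% | 2.34 | 3.51 |
| 20% | 2.83 | 4.25 |
| 30% | 3.61 | 5.42 |

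Rounded up to the next daily culture, these are 3, 3 and 4 days against a descriptive 2, and 4, 5 and 6 days against a descriptive 3. The gap is 1 to 3 days. At q = 10% much of it is rounding: the unrounded gap is 0.34 to 0.51 day.

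**3. Imperfect cultures.** If a culture misses persisting candidemia with probability f, independently each day, a patient who never clears records at least one false negative in 14 cultures with probability 1 − (1 − f)^14. For f = 0.1 this is 0.77; for f = 0.3 it is 0.99. With 20% never clearing, the share of all patients with a recorded negative is about 0.80 + 0.20 × 0.77 = 0.95, rising to nearly 1.00. Few patients are then left to censor, and the two planned medians converge.

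**4. Simulation.** 200,000 patients per scenario; exponential clearance; q = 10%, 20%, 30%; 2% per day loss; daily cultures to Day 14. Medians in days; a range covers the three values of q.

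| Culture sensitivity | m | Descriptive | Kaplan-Meier, one negative | Kaplan-Meier, first of two consecutive |
|---|---|---|---|---|
| 1.0 | 2 | 2 | 3–4 | 3–4 |
| 1.0 | 3 | 3 | 4–6 | 4–6 |
| 0.9 | 2 | 2 | 2–3 | 3–4 |
| 0.9 | 3 | 3 | 3 | 4–6 |
| 0.7 | 2 | 2 | 2 | 2–3 |
| 0.7 | 3 | 2 | 2 | 3–4 |
| 0.5 | 2 | 1 | 1 | 2 |
| 0.5 | 3 | 1 | 1 | 2 |

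At sensitivity 0.9 the descriptive and Kaplan-Meier medians agree in five of six scenarios, and at 0.7 and 0.5 in all twelve. Across sensitivities 0.5 to 0.9, requiring two negatives moves the Kaplan-Meier median 0 to 3 days later, and roughly 18% to 42% of first negatives are followed by a positive at the next culture.

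The two problems therefore do not add up. The conditional summary matters most when cultures are reliable, and the single-negative event matters most when they are not.

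**The case against.** A reader who stops at the first summary might infer that patients who never clear are left out of this endpoint altogether. The documents do not support that: the next paragraph of SAP 7.4.2.3 keeps them as censored. A reader might also infer that censoring times enter the mean as if they were clearance times. Nothing says so; the censoring sentence belongs to the Kaplan-Meier analysis.

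The descriptive table also hides less than it might. It reports n, which can be set against the size of the MITT Population. SAP 7.4.2.5 tabulates DRC reasons for failure, one of which is that cultures never turned negative. SAP 7.4.4 lists other efficacy data by patient, which is readable at about 20 patients.

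On the single negative, the SAP implements the endpoint that Protocol 7.2 names, and confirmed clearance is already required for Treatment Success at EOST and EOT. Protocol 9.2.1.2 promises only a descriptive summary, so the Kaplan-Meier estimate goes beyond it.

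All of this stands, and it lowers the severity. It does not settle which median is the main result, it does not label the conditional table, and it leaves a negative followed by a positive as clearance in both summaries. A Kaplan-Meier analysis that censors patients who die before clearing also treats them as if they could still clear, which again favours the drug.

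**Conclusion.** The point holds as a weakness in analysis choice. The descriptive mean and median favour fast clearance because they condition on having had a negative; the planned Kaplan-Meier median largely removes that bias but is presented as an addition. The single-negative event can shorten both. It would be too strong to call this a conflict between protocol and SAP.

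The size cannot be fixed from the documents. It depends on the share never clearing (10–30% assumed), culture sensitivity (0.5–1.0 assumed), independence of false negatives from day to day, and daily cultures to Day 14. The effect of censoring deaths was not quantified separately.

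Severity is minor to moderate: this is a secondary endpoint, summarised descriptively without a hypothesis test, in a single-arm study of about 20 patients with no formal sample size basis.

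**What to change.** In SAP 7.4.2.3:

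1. Make the time-to-event estimate the main summary: median with 95% confidence interval, and cumulative percentage cleared by day.
2. Do not censor patients who die before clearing. Either hold them as not cleared to the end of follow-up, or treat death as a competing event and report cumulative incidence.
3. Drop the descriptive statistics, or label them as applying among patients with a negative culture, with n/N.
4. Add one supportive analysis with the event defined as the first of two consecutive post-dose negative cultures. Saying post-dose also closes a small gap: the present definition does not state that the negative must follow the first dose, and the Day 1 Baseline culture is drawn before it.

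The cost is SAP wording and one extra table. The culture schedule in SAP 6.5.1 already supplies the data. The reported clearance time may be longer.

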5.2.3 Step-Down Therapy

The IDSA clinical practice guidelines for treatment of Candidiasis recommend that the total duration of therapy for candidemia is 14 days after documented clearance of *Candida* spp. from the bloodstream (i.e., first consecutive negative blood culture) and resolution of symptoms attributable to candidemia. Hence, the duration of antifungal treatment required to treat patients

with candidemia in this study will be driven by the time to clearance of candidemia. In 3 randomized controlled trials in candidemia and invasive Candidiasis, the median time to bloodstream infection clearance after receiving appropriate antifungal therapy was 2 to 3 days. Therefore, patients enrolled in this study may need a few additional days of fluconazole therapy (unless susceptibility results warrant alternative antifungal therapy) for a total duration of antifungal treatment of approximately 16 to 17 days. Likewise, any patients who have deep-seated sites of infections diagnosed after enrollment, while they can continue to receive APX001 study drug treatment per protocol, will require additional days of fluconazole therapy.

If appropriate, additional antifungal drug therapy with fluconazole (unless susceptibility results warrant alternative antifungal therapy) can be administered beyond 14 days of APX001. The recommended dose of fluconazole is 800 mg QD on the first day followed by 400 mg QD, for a maximum of 7 days.

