8.5.2 Subject Stopping Rule

Study treatment for an individual patient may be discontinued for lack of clinical and/or microbiological response, any adverse event, SAE, laboratory abnormality, or intercurrent illness which, in the opinion of the Investigator, indicates that continued dosing in the study is not in the best interest of the patient.

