3. SAMPLE SIZE DETERMINATION

A sample size of approximately 20 patients will be recruited in this open-label study. No formal statistical assessment for sample size determination has been performed. This sample size is considered adequate to provide the necessary data to evaluate the efficacy and safety of APX001.

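### Censoring patients who die before clearing can make the upper confidence limit and the upper part of the time-to-first-negative-culture curve too favourable to APX001; the median usually stays the same

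*SAP*

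**What the plan says.** SAP 7.4.2.3 defines the time as the "number of days from first dose date of study drug to the date of first negative blood culture plus 1". Besides descriptive statistics, it plans that "the Kaplan-Meier estimate of the median time to first negative blood culture and the associated 95% confidence interval will be presented". The method for the interval is not named. The only censoring rule is: "Patients without a negative blood culture at post-baseline visits will be censored at the last assessment date". Death has no separate provision, and the definition of the event does not mention other antifungals.

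The neighbouring endpoints do mention them. Treatment Success at EOST (SAP 6.4.1) requires "No concomitant use of any other systemic antifungal therapies through EOST", and Eradication at EOST must be "in the absence of concomitant antifungal therapy through EOST". The EOT versions (SAP 6.4.2) carry the same condition, with an exception for protocol-allowed step-down. Protocol 8.5.2 adds: "Study treatment for an individual patient may be discontinued for lack of clinical and/or microbiological response". An uncleared patient can thus leave APX001 for another drug. On size, SAP section 3 says: "A sample size of approximately 20 patients will be recruited in this open-label study".

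**The concern.** Censoring is harmless when the censored patient has the same prospects as those who remain. A patient who has died uncleared has no prospect of clearing, so death is a competing event. Kaplan-Meier nevertheless passes that patient's weight to the survivors, and the curve then describes clearance as if nobody could die first.

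The second gap works in the same direction. Cultures continue at EOST, EOT, the two follow-up visits and Early Termination. A first negative culture obtained after a switch to another antifungal would count as clearance, although the same patient fails Treatment Success and Eradication.

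This is the first-listed secondary efficacy endpoint. With about 20 patients and no control arm, one to three patients can decide where the upper limit falls, and the patients affected are those whom APX001 did not clear.

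**Working it through.** **No planned figure to reproduce.** The documents state no expected median, event count, death rate or rescue rate for this endpoint. Protocol 5.2.3 reports from outside trials that "the median time to bloodstream infection clearance after receiving appropriate antifungal therapy was 2 to 3 days", as background for treatment duration. Death rates, clearance rates and the log-log interval below are therefore assumptions.

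**Step 1: a constructed example that can be checked by hand.** Take 20 patients. Six clear on Day 2, five on Day 3, three on Day 4, two on Day 5 and one on Day 6 (17 in all). Three die uncleared, with last cultures on Days 2, 3 and 4.

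Proportion not yet cleared:

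| Day | SAP rule (deaths censored) | Death as competing event |
|---|---|---|
| 2 | 14/20 = 0.700 | 14/20 = 0.70 |
| 3 | 0.700 × 8/13 = 0.431 | 9/20 = 0.45 |
| 4 | 0.431 × 4/7 = 0.246 | 6/20 = 0.30 |
| 5 | 0.246 × 1/3 = 0.082 | 4/20 = 0.20 |
| 6 | 0 | 3/20 = 0.15 |

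The median is Day 3 both ways. The SAP curve ends at 100% cleared; in fact 17/20 = 85% cleared.

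The upper limit of the median is the first day on which the upper log-log bound of the proportion S not yet cleared is at or below 0.5. That bound is exp(−exp(ln(−ln S) − 1.96 × √V / |ln S|)), where V is the Greenwood sum. On Day 4:

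- SAP rule: V = 6/(20×14) + 5/(13×8) + 3/(7×4) = 0.1766, and the bound is 0.459. The upper limit is Day 4.
- Competing event: V = 0.70/(20×0.30) = 0.1167, and the bound is 0.501, just above 0.5. On Day 5 it is 0.393. The upper limit is Day 5.

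The Day 4 result is close to the line, and other arrangements of three deaths leave the limit where it was. Hence the simulation.

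**Step 2: simulation of deaths alone.** Each trial has 20 patients. Each patient dies uncleared with the stated probability, with the last culture on one of Days 2 to 6. The others clear with a constant daily probability from Day 2: 0.50 (as-written median about 3 days) or 0.30 (about 4 days).

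| Dying uncleared | Upper limit lengthens, median about 3 | Upper limit lengthens, median about 4 |
|---|---|---|
| 5% | 7% of trials | 23% |
| 10% | 21% | 42% |
| 15% | 35% | 59% |
| 20% | 47% | 75% |

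The median changed in 7% of trials or fewer in every setting. On average the SAP curve ended at 93% to 99% cleared when 79% to 95% had cleared. No trial moved against APX001. Repeating the simulation with 4,000 trials per setting reproduced the table to within 2 percentage points.

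**Step 3: adding clearance on another antifungal.** A second set of simulations assumed a true median of 2 or 3 days, uncleared death at 1% to 6% per day, and a switch at 0% to 30% per day from Day 4. It treated both death and the switch as competing events. Against the SAP rule, the median changed in 0% to 15% of trials and the upper limit in 12% to 89%, again never against APX001. The upper ends of these ranges need heavy rates: roughly 3 to 4 deaths and 3 to 4 switches among 20 patients.

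**The case against.** **A reader might infer that the reported median is too favourable.** The documents do not support that. Protocol exclusion 6 keeps out patients expected to live less than 72 hours, so few uncleared deaths should precede a median of 2 to 4 days, and clearance after a switch tends to come later still. The calculations agree: the median usually stays put.

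**The inputs are assumed.** This stands. No death or rescue rate is given, and at 5% uncleared deaths with fast clearance little moves. The effect also shrinks if those who die are censored late, because the simulation puts their last cultures on Days 2 to 6.

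**The antifungal gap may be small, and may be a choice.** Protocol 5.6.2 bars other systemic antifungals for candidemia during APX001, and daily cultures are required only during study drug treatment, so few such events may be captured. Counting every negative culture regardless of later drugs is a legitimate treatment-policy definition, and differing from Treatment Success is not in itself an error. What remains is that the SAP does not say which definition it intends.

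**A reader might also infer that failures are hidden or that a benchmark test is biased.** Neither follows. The primary endpoint counts death and other antifungals as failure, SAP 7.4.2.5 tabulates the reasons for failure, and Day 30 survival is reported separately. The endpoint is descriptive, and no comparison with the 2 to 3 days is planned.

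None of this corrects the curve or the interval. SAP 7.1.2 keeps dropouts in the efficacy denominator but gives no rule for time-to-event data.

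**Conclusion.** The point holds for the upper 95% limit and the upper part of the clearance curve. As written, uncleared deaths are censored as uninformative, and the resulting error can only favour APX001. Its size depends on how many patients die uncleared and how early they were last assessed, which the documents do not give. At an assumed 10% (two of 20 patients), the upper limit lengthens in 21% to 42% of trials. The median is largely safe, and the primary endpoint is untouched. The missing condition on other antifungals is a secondary point: it adds to the same bias if such cases occur, and it calls for a stated rule. The change is worth making before database lock because it corrects an explicit analysis rule at little cost.

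**What to change.** In SAP 7.4.2.3:

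- Treat death before a negative culture as a competing event. Report the cumulative incidence of clearance and read the median and its 95% interval from that curve, naming the interval method. Keeping uncleared deaths in the risk set to the longest follow-up time gives the same curve, provided that no living uncleared patient is censored earlier.
- Censor only patients who are alive and uncleared, at the date of the last blood culture.
- State that starting another systemic antifungal for candidemia before clearance is also a competing event, in line with Eradication. Say how step-down therapy begun before a negative culture is classed, since the EOST and EOT definitions differ on it. Give the version that counts all cultures (treatment policy) as a sensitivity analysis.
- Report the numbers cleared, died uncleared and rescued uncleared.

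The cost is one SAP paragraph and minor programming, with no new data. SAP section 9, which now declares no changes from the protocol's analysis, should be checked against the revised text. The price for the sponsor is an upper limit that may be longer or not reached.
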